## **DESCRIPTIVE ANALYSES**

The proposed tables to be populated during the analysis can be found in the appendix

## **Participant flow**

Participant throughput will be summarized in a CONSORT diagram.

## **Representativeness of sample**

Information unavailable to make this comparison

## **Baseline comparability of randomised groups**

See table 1 in the appendix for the variables to be used in these comparisons.

### **Demographics**

### **Prior and concurrent medications**

### **Baseline and screening conditions**

### **Baseline medical history**

### **Baseline physical exam**

### **Cluster characteristics if cluster randomised**

### **Characteristics of care providers where applicable**

## **Comparison of losses to follow-up**

See table 2 in the appendix

### **Comparison of compliance to treatment and protocol**

Compliance to treatment will be summarised as the number of returned used sachets of medication.

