## **STUDY OBJECTIVES AND ENDPOINTS**

### **Study objectives**

#### **Primary objectives**

1.To determine whether intermittent treatment with oral montelukast in preschool children reduces the need for unscheduled medical attention (GP visit, hospital attendance, hospital admission) for wheeze.

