#### Investigational Medicinal Product (IMP) usage:

- The number of IMP initiations (whether for wheeze or cold).
- Mean sachets (IMP use) per episode (wheeze or cold) as recorded on the diary card
- Compliance calculated from diary card, number dispensed and number returned

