### ***Medication use IMP***

Diary card: Date

Diary card: Wheeze in last 24 hours (Yes/No)

Diary card: Cold in last 24 hours (Yes/No)

Diary card: Trial medicine used today (Yes/No)

Phone call data: Number of IMP initiations

Phone call data: Total days used

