#### **Per protocol population**

The Per Protocol (PP) sample is defined as the available case sample with those participants who discontinue IMP or were randomised incorrectly being excluded.

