### **Method for handling non-adherence**

Analysis of all primary and secondary outcomes will be performed on an intention-to-treat basis. A Complier Average Causal Effect (CACE) analysis and per protocol analysis will also be conducted for the primary analysis.

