### **Primary analysis**

The primary analysis will be a Poisson regression model with the follow up time of each individual fitted as an exposure variable and with a random effect for individual to account for overdispersion.

The incident rate ratio (IRR) for the treatment effect and corresponding 95% confidence interval will be presented. An IRR of less than 1 indicates a benefit of Montelukast in reducing the rate of unscheduled medical attendance needed.

Assumption checks and actions to be taken if assumptions do not hold

The fit of the model will be compared to a model without a random effect using the likelihood ratio test, and the fit will be assessed using diagnostic plots (residuals versus fitted values), alternative distributions to the Poisson such as the Negative binomial or removal of the random effect shall be considered where necessary for improved fit.

Other analysis supporting the primary (inc. sensitivity analyses)

The primary analysis will be performed on the per-protocol population and using a CACE analysis.

It will be repeated replacing any stratification factors that were incorrectly defined at randomisation with the corrected values (see section 1.4).

It will be repeated with exclusion of 11 incorrectly randomised participants (see section 1.4).

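### For a drug taken only for colds or wheeze, a count of used sachets measures illness more than compliance, and the planned CACE has no complier definition to use instead

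*SAP*

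**What the plan says.** The treatment is intermittent. The primary objective is "To determine whether intermittent treatment with oral montelukast in preschool children reduces the need for unscheduled medical attention", and the IMP usage outcomes count "The number of IMP initiations (whether for wheeze or cold", so a cold or wheeze is the occasion for use.

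Compliance appears in two places, on two bases:

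- *Comparison of compliance to treatment and protocol*, under the descriptive analyses: "Compliance to treatment will be summarised as the number of returned used sachets of medication". This is a raw count with no denominator.
- *Investigational Medicinal Product (IMP) usage*, under the secondary outcomes: "Compliance calculated from diary card, number dispensed and number returned". This adds the diary card and the dispensed count but gives no formula.

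The section on non-adherence states: "A Complier Average Causal Effect (CACE) analysis and per protocol analysis will also be conducted for the primary analysis". The supporting analyses of the primary outcome repeat it: "The primary analysis will be performed on the per-protocol population and using a CACE analysis". Neither place defines a complier, a cut-off, an estimator or its assumptions. The per-protocol set does not use sachets; it is "the available case sample with those participants who discontinue IMP or were randomised incorrectly being excluded".

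The diary fields for IMP include wheeze and cold by day, and "Diary card: Trial medicine used today (Yes/No". The section on derived variables adds that children not taking IMP do not complete diary cards.

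**The concern.** With an as-needed drug, compliance means taking it when the occasion arises. A sachet count leaves out the occasion. A low count cannot separate a child who stayed well from one who was ill and untreated, and a high count mostly marks a child who was often or long ill. The count therefore does not answer the SAP's objective of describing compliance. Dividing by sachets dispensed does not repair this, because the dispensed number measures supply and not occasions for use.

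The SAP also lists returned used sachets in Table 4, with a rate ratio between arms. The same quantity would then serve as a measure of compliance and as a result of treatment.

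The CACE is where this could mislead. Its complier rule is open, and the statistical analysis is to be run unblinded. If the sachet count, or its ratio to sachets dispensed, were adopted by default, the sicker children would be labelled compliers. Complier status would then be bound up with the primary outcome.

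**Working it through.** The SAP gives no compliance figure to reproduce, so the check combines an identity, a closed-form result and a simulation.

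**Inputs from the SAP** (sample size section): mean 0.76 and SD 1.22 attacks, and a 33% drop to 0.51 in attacks requiring medical attention. As a check on these inputs, the two-means formula gives 2 x (1.960 + 1.282)^2 x 1.22^2 / 0.25^2 = 501 per arm, or 1002 in total. Dividing by 0.94 for 6% loss gives 1066. The SAP states 1050 from its own simulation, so the inputs are coherent.

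**Assumptions not in the SAP:** gamma-Poisson episodes; 1, 3 or 5 episodes per attendance; 5 or 10 sachets per treated episode; treatment cuts attendance by 33% in treated episodes and leaves the number of episodes unchanged; adherence is either perfect, or uniform from 30% to 100% and independent of illness. Each setting used 400,000 children.

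**Step 1, identity.** Sachets used = episodes x proportion treated x sachets per treated episode. Only the middle term is adherence in starting treatment.

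**Step 2, zero counts under perfect adherence.** Dispersion k = (1.22^2 - 0.76) / 0.76^2 = 0.7284 / 0.5776 = 1.26. The chance of no episode is (1 + k x m)^(-1/k), where m is the mean number of episodes:

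| Episodes per attendance | m | No episode, so no sachets |
|---|---|---|
| 1 | 0.76 | 59% |
| 3 | 2.28 | 34% |
| 5 | 3.80 | 25% |

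The simulation gives the same percentages. All these children are adherent, and all score zero.

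**Step 3, what the count tracks.** With perfect adherence, sachets correlate 0.95 to 0.99 with episodes, and 0.75 to 0.98 with the primary outcome on placebo. With variable adherence, sachets correlate 0.81 to 0.89 with episodes, but the Spearman correlation with true adherence is only 0.15 to 0.21.

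**Step 4, a CACE with a sachet cut-off.** Take a complier to be a child at or above the median count among users, and use the Wald estimator (ITT difference divided by the proportion of compliers in the active arm). Every child is adherent, so the true effect is the ITT effect, about -0.25.

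- Labelled compliers: 21% to 39% of children.
- Placebo attendances: 1.61 to 2.62 in labelled compliers, 0.22 to 0.27 in the rest.
- Wald CACE: -0.65 to -1.17. At the extremes, 0.646 / 0.253 = 2.6 and 1.173 / 0.247 = 4.7 times the true effect.

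Part of this gap arises because labelled compliers are sicker and have more to gain, but not all of it. With 1 episode per attendance and 5 sachets, the true effect in labelled compliers is 0.33 x 2.46 = 0.81 fewer attendances, and the Wald estimate is 1.11. The implied rate ratio is (2.46 - 1.11) / 2.46 = 0.55, where the true one is 0.67. The excess comes from children below the cut-off, who also took the drug and benefited, so the exclusion restriction fails.

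**Step 5, any sachet versus none.** Under perfect adherence this rule gives -0.34 to -0.61. The contrast is identifiable, but it describes children who fell ill and used the drug, not adherent children.

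**The case against.** A reader might infer that the SAP builds its CACE on sachet counts. It does not say so. The count sits under descriptive analyses, and the two places that name the CACE refer neither to it nor to sachets. What stands is that the CACE has no complier definition and that the SAP's only explicit compliance formula is unsuitable for one.

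It can also be said that other material is available. The IMP usage list names the diary card. Table 6 plans sachets per episode, which is free of illness frequency. Withdrawal from treatment is recorded. This is fair, and it means that a usable measure may be within reach. But the diary-based measure has no formula, sachets per episode is labelled as use and may miss untreated episodes, and none of these is assigned to the CACE.

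A third reading is that a 33% effect would make the active arm look 33% less compliant. The SAP does not support this. Its 33% concerns attacks requiring medical attention, and it assumes no such drop in the colds and wheeze that trigger IMP.

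Nor can it be said that no CACE is possible, since the any-versus-none contrast is identifiable. What that contrast means would have to be stated.

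Finally, a per-episode measure may not be feasible. The remark that diary cards are not completed by those not taking IMP may concern only children withdrawn from medication. If it applies more widely, untreated episodes leave no record and the proportion would be near 100% by construction. Phone-call IMP initiations count treated episodes only and cannot supply the denominator. This limit stands and is carried into the fix.

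**Conclusion.** The point holds in this form. The stated compliance measure mainly reflects illness, the two descriptions of compliance differ, and the CACE has no complier rule, so a sachet-based rule is an unsuitable default. The direction of the problem follows from as-needed use. The size does not come from the SAP: the figures of 25% to 59% with zero sachets, and of 2.6 to 4.7 times the true effect, depend on the assumed episodes per attendance, sachets per episode and adherence pattern, and on an assumed median cut-off and Wald estimator.

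The consequence is limited. A reader might infer that the trial's main conclusion is at risk, but primary and secondary outcomes are analysed by ITT, the per-protocol set does not use sachets, and the CACE is a supporting analysis. The change should be made, but the primary analysis does not depend on it.

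**What to change.** Before unblinding:

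1. Reconcile the compliance wording in the IMP usage outcomes and in the compliance comparison section, so that one definition applies throughout.
2. Report sachet counts as drug use only, as Tables 4 and 6 already allow.
3. Define compliance relative to opportunity: the proportion of diary-recorded wheeze or cold episodes (or symptomatic days) on which the trial medicine was marked as used.
4. Report children with no recorded episode separately, as compliance not assessable. Counting them as compliant would move the healthiest children into the complier group and tie complier status to illness again.
5. State that the CACE complier rule will not be a sachet count or a ratio to sachets dispensed, and give the rule, the estimator and its assumptions.
6. Establish whether untreated episodes are recorded on the diary. If they are not, say so and drop the CACE.

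The cost is SAP wording and one derived variable from fields already collected. The downside is that the measure depends on diary completeness.

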### **Emergency or accidental unblinding of randomised treatment**

All unblindings will be summarised by treatment group

## **INTERIM ANALYSES AND SAFETY MONITORING ANALYSES**

### **Purpose of interim analyses**

No interim analyses of the data were planned or conducted.

### **Monitoring plan**

A Data Monitoring Committee was initiated at the beginning of the study. This committee met three times during the course of the study and saw accumulating data by treatment group on recruitment, safety and efficacy. All data was presented descriptively with no hypothesis testing.

### **Stopping rules**

Not applicable

### **Measures taken to minimize bias**

Not applicable

### **Adjustment for p-values**

Not applicable

### **Interim analysis for sample size adjustment**

Not applicable

## **ANALYSIS OF PRIMARY OUTCOME**

### **Definition of outcome measure**

The primary outcome for each participant is the total number of unscheduled medical attendances over the course of the trial.

### **Descriptive statistics for outcome measure**

The primary outcome will be summarised for each treatment group as the total number of events and corresponding median length of follow up time per treatment group.

Data will be presented as mean (sd) or median (interquartile range) depending upon the distribution of the data.

### **Primary analysis**

The primary analysis will be a Poisson regression model with the follow up time of each individual fitted as an exposure variable and with a random effect for individual to account for overdispersion.

The incident rate ratio (IRR) for the treatment effect and corresponding 95% confidence interval will be presented. An IRR of less than 1 indicates a benefit of Montelukast in reducing the rate of unscheduled medical attendance needed.

Assumption checks and actions to be taken if assumptions do not hold

The fit of the model will be compared to a model without a random effect using the likelihood ratio test, and the fit will be assessed using diagnostic plots (residuals versus fitted values), alternative distributions to the Poisson such as the Negative binomial or removal of the random effect shall be considered where necessary for improved fit.

Other analysis supporting the primary (inc. sensitivity analyses)

The primary analysis will be performed on the per-protocol population and using a CACE analysis.

It will be repeated replacing any stratification factors that were incorrectly defined at randomisation with the corrected values (see section 1.4).

It will be repeated with exclusion of 11 incorrectly randomised participants (see section 1.4).

## **ANALYSIS OF SECONDARY OUTCOMES**

### **Definition of outcome measure**

individual type of medical attendance: (hospital admission, hospital attendance (a&e), and GP visit)

Duration (in days) of hospital admission

Number of wheeze episodes

Total duration of wheeze episode

The number of steroid (OCS) courses per year

The number of IMP courses per year

first hospital admission

first hospital attendance (A&E)

first GP visit

first episode of wheeze

proportion receiving no steroids (OCS) vs. any during the trial

Proportion starting steroids (ICS) during the trial

Salbutamol use per year

Salbutamol use per episode of wheeze per year

### **Descriptive statistics for outcome measure**

Each outcome will be summarised for each treatment group as the total number of events or average duration of episode.

Data will be presented as mean (sd) or median (interquartile range) depending upon the distribution of the data.

### **Secondary analysis**

The primary analysis will be repeated for each of the following secondary outcomes:

individual type of medical attendance: (hospital admission, hospital attendance (a&e), and GP visit)

Duration (in days) of hospital admission

Number of wheeze episodes

Duration of wheeze episode

The number of steroid (OCS) courses per year

The number of IMP courses per year

Time to event data will be summarised using Kaplan Meier plots. The treatment effect will be evaluated using a Cox regression model. The Hazard Ratio (HR) for the treatment effect and corresponding 95% confidence interval will be presented. A

HR of less than 1 indicates a benefit of Montelukast in reducing the time to first event.

first hospital admission

first hospital attendance (A&E)

first GP visit

first episode of wheeze

Binary outcomes will be analysed with logistic regression

proportion receiving no steroids (OCS) vs. any during the trial

Proportion starting steroids (ICS) during the trial

Assumption checks and actions to be taken is assumptions do not hold

The assumption of proportional hazards for the cox regression model will be checked using the methods proposed by Grambsch and Therneau. If this assumption is violated, alternative methods will be used.

See section 8.4 for Poisson regression assumption checks.

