**Medication use**

Steroids (OCS):

- The number of courses per year (and total number of days) as recorded on the diary card. Each mention of use on a separate diary card indicates a course.
- The proportion receiving none vs. any during the trial as recorded on the diary card or in the phonecall data.

Steroids (ICS):

- Proportion starting ICS during the trial as recorded on the diary card or phonecall data (baseline data (T2) indicates whether child was on ICS at the start of the trial)

Salbutamol:

- Total number of puffs overall per episode of wheeze as recorded on the diary card
- Total number of puffs (Salbutamol use per year)

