### **Methods for withdrawals, loss to follow-up and missing data**

Those participants who withdraw and provide permission to use their data will be included in the analysis up to the point of withdrawal.

For the primary outcome phonecall data, at the time of writing (prior to unblinding) we have:

Full 12 months data on 1134/1347(84%)

29/1347 (2%) participants withdrew before the first 2 month phonecall and have no data collected as expected

12/1347 (0.9%) do not have any follow up data and this is being queried with the sites

Partial follow up data is available for 172 (13%). 44 of these participants did not formally withdraw from follow up. This is being queried with the sites

After data cleaning we expect the levels of missing data to improve. Due to these relatively low levels of missing data, and that the follow up time for each participant is to be included in the analysis no imputation of the missing data will be performed

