## **Derived and computed variables**

All derived and computed variables will be documented in the analysis programmes. The primary outcome is a summation of all types of medical attendances across the entire trial, for each participant.

The primary outcome, and the breakdown of unscheduled medical opinion, will be taken solely from the phone call data as this data has been confirmed against clinical records.

Medication use data may be recorded on either the phone call CRF and/or the diary card. A medication will be defined as being used if it appears in either of these two records.

Medical attendance data was collected strictly within 12 months, as calculated from the date of randomisation. Participants who do not experience an event are censored at exactly 12 months of follow up or the point of withdrawal from follow up. Any diary data collected outside of the 12 month follow up will be excluded from the analysis. Participants who do not experience episodes of cold or wheeze will be censored at the point of 12 months from randomisation or withdrawal from medication, as diary cards are not completed for those not taking IMP.

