**Table 6: Medication usage**

ITT population	Montelukast N=	Placebo N=	IRR or OR (95% CI)	p-value
Steroids (OCS)				
 Number of courses, mean (SD)				
 Proportion receiving OCS, N (%)				
Steroids (ICS)				
 Proportion starting, N (%)				
Salbutamol				
 Number of puffs used per episode, mean(SD)				
Total puffs used per year				
Investigational Medicinal Product				
 Number of initiations, mean (SD)				
 Number of sachets per episode, mean (SD)				
Number of sachets used per year				

Data are analysed using Poisson regression with fixed effects for stratification factor and treatment group and a random effect for individual to account for overdispersion with follow up time fitted as the exposure.

Data are analysed using logistic regression with fixed effects for stratification factor and treatment group

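### The logistic models for any oral steroid use and for starting inhaled steroids ignore follow-up time, so the SAP's reason for leaving incomplete follow-up untreated does not cover them

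*SAP*

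**What the plan says.** The Medication use part of the SAP's secondary outcomes defines two binary steroid outcomes: for OCS, "The proportion receiving none vs. any during the trial as recorded on the diary card or in the phonecall data"; for ICS, "Proportion starting ICS during the trial as recorded on the diary card or phonecall data". The section on derived variables sets the coding rule: "A medication will be defined as being used if it appears in either of these two records". It sets no minimum period of observation for a child to count as a non-user.

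Under Secondary analysis, "Binary outcomes will be analysed with logistic regression". The second footnote of Table 6 gives the model in full: "Data are analysed using logistic regression with fixed effects for stratification factor and treatment group". The first footnote, for the count outcomes in the same table, adds what the second lacks: "with follow up time fitted as the exposure".

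The section on withdrawals, loss to follow-up and missing data keeps withdrawn children in the analysis up to withdrawal if they permit use of their data. It cites the low level of missing data and adds that "the follow up time for each participant is to be included in the analysis no imputation of the missing data will be performed". No sensitivity analysis is planned for secondary outcomes.

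**The concern.** The decision to do nothing further about incomplete follow-up rests partly on follow-up time being in the model. That holds for the Poisson models, and the Cox models deal with short follow-up by censoring. The two logistic models do neither. Under the coding rule, a child who leaves after two months with no steroid record enters as a non-user with the same weight as a child observed for the full year.

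Two things follow. Each arm's proportion falls below its 12-month value. And if one arm is followed for less time, the odds ratio moves in favour of that arm even when treatment does nothing. Both odds ratios serve the objective on alternative medications, and both carry a p-value read at 5%. Starting ICS has no other analysis in the SAP that would show the problem.

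**Working it through.** **Inputs from the SAP (missing-data section).** Full 12-month phone-call data 1134; partial 172; no data 29 (withdrew before the first call) and 12 (under query); total 1347.

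**Reproducing the SAP's figures.** 1134 + 172 + 29 + 12 = 1347. 1134/1347 = 84.2%, 172/1347 = 12.8%, 29/1347 = 2.2%, 12/1347 = 0.9%. These agree with the stated 84%, 13%, 2% and 0.9%. Children without data: 29 + 12 = 41 (3.0%). Incomplete in all: 172 + 41 = 213 (15.8%).

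**Assumptions (not in the SAP).**
- True 12-month risk p of 20%, 40% or 60%, the same in both arms, with a constant rate.
- Partly followed children are seen for half a year on average.
- One fifth of incomplete cases have no data (41/213 = 19%) and are left out.
- The splits of incomplete follow-up by arm given below.

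**Formula.** With L = −ln(1 − p), half-year risk h = 1 − exp(−0.5L) and incomplete fraction q in an arm:

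P(any use recorded) = [(1 − q)·p + 0.8q·h] / (1 − 0.2q)

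For p = 20%, 40%, 60%, h = 10.6%, 22.5%, 36.8%.

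**Balanced loss, q = 15.8% in both arms.** At p = 40%: (0.842 × 0.400 + 0.1264 × 0.2254)/0.9684 = 0.3653/0.9684 = 37.7%. A true 40% reads as 37.7% in each arm, and the odds ratio is 1.00.

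**Unbalanced loss, no treatment effect.** Worked case, p = 40%, 12.0% vs 19.6%: the arms read 38.3% and 37.1%, and OR = (0.3828/0.6172)/(0.3715/0.6285) = 1.05.

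| Incomplete, numerator arm vs other arm | p = 20% | p = 40% | p = 60% |
|---|---|---|---|
| 15.8% vs 15.8% | 1.00 | 1.00 | 1.00 |
| 13.8% vs 17.8% | 1.02 | 1.03 | 1.03 |
| 12.0% vs 19.6% | 1.04 | 1.05 | 1.06 |
| 10.0% vs 21.6% | 1.06 | 1.08 | 1.10 |

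Reversing the imbalance inverts the ratios, for example 0.96 to 0.94 for 19.6% vs 12.0%.

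**How plausible the gaps are.** With about 673 children per arm and 15.8% incomplete, the standard error of the difference between arms is √(2 × 0.158 × 0.842/673) = 0.020. The three unbalanced rows are gaps of 4.0, 7.6 and 11.6 points, or 2.0, 3.8 and 5.8 standard errors.

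**Type I error.** A parallel calculation took 13.2% partial (172/1306, children without data excluded), half a year followed and 653 children per arm. True two-sided error rises from 5% to about 5.5–7% for a 5-point gap in partial follow-up, and to about 7–14% for a 10-point gap.

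**Does the remedy work?** A simulation with 400,000 per arm, no effect, 18% vs 8% partial and dropout times uniform over the year gave logistic odds ratios of 0.94 (p = 20%) and 0.93 (p = 40%). A complementary log-log model with log follow-up time as offset gave 1.00 in both.

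**The case against.** The strongest reply is that the effect is small and conditional. This is a double-blind trial with identical packaging, and nothing in the SAP shows that follow-up differs by arm. A chance gap of two standard errors moves a null odds ratio only to 1.02–1.03, while the standard error of the log odds ratio is about 0.11–0.14. Table 2 will show withdrawals by arm. The SAP expects missing data to fall after cleaning, with 12 no-data and 44 partial cases still under query. The outcome is worded as use during the trial, so a crude proportion is a legitimate description. OCS also has a course count analysed with follow-up as exposure. All of this stands, and it limits the point to a modest one.

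It does not remove it. Withdrawal reasons on the SAP's own list, such as perceived lack of efficacy or an adverse event, can differ by arm under blinding. Cleaning cannot restore follow-up for children who truly left. Starting ICS has no time-adjusted companion. And the stated rationale still does not fit these two models.

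A reader might also infer that the 41 children without data are counted as non-users, because Table 6 is headed as intention-to-treat. No sentence says so: the SAP rules out imputation and also defines an available-case set. Coding them as non-users would raise the ratios to 1.06–1.10 for 12.0% vs 19.6% and to 1.09–1.15 for 10.0% vs 21.6%, but those figures rest on a rule the SAP does not state.

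**Conclusion.** The point holds in a limited form. The two logistic models take no account of follow-up time, the rationale in the missing-data section does not cover them, and no sensitivity analysis makes up for it. Relative to 12-month use, both proportions will be understated; on the assumptions above a true 40% reads as about 37.7%.

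It would go too far to say that dropout will appear as a treatment effect. With no true effect the odds ratio stays at 1.00 under equal follow-up and departs from 1 only if follow-up differs by arm, which the SAP does not report. The sizes, about 1.04–1.06 and 1.06–1.10 for the two larger assumed gaps, depend on an assumed steroid-use rate, an assumed half-year mean follow-up for partial cases, and arm gaps that would be large for chance alone. The 12.8% partial figure concerns phone-call data. Diary follow-up may be shorter, because diary cards stop when trial medication stops. Starting ICS is the outcome most exposed. The change is worth making because follow-up time is already derived for the other models.

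**What to change.** Analyse both outcomes with a complementary log-log model, log(follow-up time) as offset and the same stratum and treatment terms, reported as a hazard ratio:

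log(−log(1 − P)) = log(t) + intercept + stratum + treatment

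This needs no start date for the medication, which suits mentions in the phone-call data, where the SAP lists no medication date. Keep the crude N (%) in Table 6 and, if wanted, the logistic odds ratio as a supporting result.

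- **Clock.** Use phone-call follow-up for t. Add a check that ends at withdrawal from trial medication, when diary cards stop.
- **Children with no observed time.** Exclude them from these two models and give their number by arm in a footnote.
- **Missing-data section.** Say how the follow-up-time rationale applies to each type of model.

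Cost: a changed model line and footnotes, plus one check on the second clock. The reported measure changes from an odds ratio to a hazard ratio. The model assumes a roughly constant rate over the year and non-informative dropout; it removes only the part of the bias that comes from unequal observation time.
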